Persistence ^c	The follow-up culture at the site of infection taken at the EOT visit (or, if not available, from the last available culture after at least 48 hours of IV study therapy) grows the pathogen found at study entry.
Super infection	The follow-up culture at the site of infection taken at the EOT visit (or, if not available, from the last available culture after at least 48 hours of IV study therapy) grows a pathogen other than a baseline pathogen during the course of IV study therapy OR emergence during IV study therapy of a new pathogen at a distant sterile site along with worsening signs and symptoms of infection.
Indeterminate	
 a) Entry culture at the site of infection either not obtained or no growth; OR b) Follow-up cultures are not available from the site of infection due to subject death or withdrawal from study; OR c) Microbiological data are incomplete; OR d) Assessment not possible due to protocol violation; OR e) Any other circumstance which makes it impossible to define the microbiological response

^a A microbiological response rating will be determined separately for each pathogen isolated at baseline. If a new/emergent pathogen is identified at this visit which was not identified at baseline, the microbiological response rating will be considered “super infection” for any new/emergent pathogen isolated after initiation of IV study therapy.
^b A favorable overall microbiological response at EOT requires “eradication” or “Presumptive eradication” of all baseline pathogens.
^c If a subject is discontinued from IV study therapy due to clinical failure (i.e., unfavorable clinical response), but persistence of the admission pathogen is not confirmed by culture results or no culture is obtained at the time of clinical failure, the admission pathogen will be presumed to have persisted.

Table 5 Definitions of the By-Pathogen Microbiological Response for cIAI at the TOC Visit

Microbiological Response ^{a,b}	Response Definition
Sustained eradication ^c	The follow-up culture at the site of infection taken at TOC visit, shows eradication of the pathogen found at study entry.
Presumptive eradication	Absence of material to culture from the site of infection in a subject who had responded clinically to treatment.

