Persistence	The follow-up culture at the site of infection taken at TOC visit grows the pathogen found at study entry. These subjects are carried forward with this status from the EOT visit otherwise it meets the criteria for 'New infection' or 'Recurrence' to those 2 follow up visit.
New Infection	Eradication of the original pathogen from the site of infection followed by replacement (at the same site and after completion of IV study therapy) by a new species or by a new serotype or biotype of the same organism in the presence of signs or symptoms of infection. If a pathogen was isolated from a site distant to the primary infection after IV study therapy has been completed, then this is also designated as a new infection.
Recurrence	The follow-up culture from the site of infection taken anytime after documented eradication at the EOT visit grows the original pathogen.
Indeterminate	
 a) Follow-up culture is not available at the TOC visit due to subject death or withdrawal from study; OR b) Microbiological data are incomplete; OR c) Assessment not possible due to protocol violation; OR d) Any other circumstance which makes it impossible to define the microbiological response

^a A microbiological response rating will be determined separately for each pathogen isolated at baseline. If a new/emergent pathogen is identified at this visit which was not identified at baseline, the microbiological response rating will be considered a "new infection" for any new/emergent pathogen isolated after initiation of IV study therapy.

^b A favorable overall microbiological response at TOC visit requires "sustained eradication" or "Presumptive eradication" of all baseline pathogens.

^c A microbiological response of "sustained eradication" at TOC is used when the microbiological response assessment at EOT visit is also "eradication".

4.2.3.2.1.2.2 Microbiological Response for cUTI

The following tables are for the definitions of Microbiological Response for cUTI, as described in [Table 6](#) (for the EOT visit) and [Table 7](#) (for the TOC visit).

Table 6 Definitions of the By-Pathogen Microbiological Response Rating for cUTI at the EOT Visit

Microbiological Response ^{a,b}	Response Definition
Eradication	A urine culture taken at the EOT visit ^d shows eradication of the uropathogen (e.g., $\geq 10^5$ CFU/mL is reduced to $< 10^4$ CFU/mL) found at study entry.

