Persistence ^c	A urine culture taken at the EOT visit ^d grows a uropathogen (at $\geq 10^4$ CFU/mL) found at study entry.
Super infection	An infection-site culture grows a uropathogen (at $\geq 10^5$ CFU/mL) other than a baseline pathogen during the course of IV study therapy OR emergence during IV study therapy of a new pathogen at a distant (non-urine), sterile site along with worsening signs and symptoms of infection.
Indeterminate	
 a) Follow-up urine culture is not available at the EOT visit due to subject death or withdrawal from study; OR b) Microbiological data are incomplete; OR c) Assessment not possible due to protocol violation; OR d) Any other circumstance which makes it impossible to define the microbiological response

^a A microbiological response rating will be determined separately for each pathogen isolated at baseline. If a new/emergent pathogen is identified at this visit which was not identified at baseline, the microbiological response rating will be considered “super infection” for any new/emergent pathogen isolated after initiation of IV study therapy.

^b A favorable overall microbiological response at EOT requires “eradication” of all baseline pathogens.

^c If a subject is discontinued from IV study therapy due to clinical failure (i.e., unfavorable clinical response), but persistence of the admission pathogen is not confirmed by culture results or no culture is obtained at the time of clinical failure, the admission pathogen will be presumed to have persisted.

^d If a culture is not available at EOT, an assessment at this visit can be made from the last available urine culture which was collected after at least 48 hours of IV study therapy.

Table 7 Definitions of the By-Pathogen Microbiological Response for cUTI at the TOC Visit

Microbiological Response ^{a,b}	Response Definition
Sustained eradication ^c	A urine culture taken at the TOC visit still shows eradication of the uropathogen (e.g., $\geq 10^5$ CFU/mL is reduced to $< 10^4$ CFU/mL) found at study entry.
Persistence	A urine culture taken at the TOC visit grows a uropathogen (at $\geq 10^4$ CFU/mL) found at study entry.
New Infection	A uropathogen, other than a microorganism found at baseline is present in the urine (at a level $\geq 10^5$ CFU/mL) any time after IV study therapy is finished; OR A pathogen is isolated from a distant (non-urine), sterile after IV study therapy has been completed.

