2. Anatomical

Subject has at least one of the following conditions associated with a risk for developing cUTI:

- Indwelling urinary catheter or other urinary bladder instrumentation
- Urinary retention (at least 100 mL of residual urine after voiding)
- Neurogenic bladder
- Obstructive uropathy (nephrolithiasis, fibrosis or prostatic hypertrophy)
- Azotemia

OR,

Subject has pyelonephritis and normal urinary tract anatomy.

3. Microbiological

Subject has a positive urine culture at baseline as defined below:

- $\geq 10^5$ CFU/mL of uropathogen either from a mid-stream clean catch (MSCC) or indwelling catheter urine specimen, OR
- $\geq 10^4$ CFU/mL of uropathogen either from a MSCC or indwelling catheter urine specimen if blood culture is also positive

NOTE: For subjects with an indwelling catheter, samples should be collected following the placement of a new catheter. If the placement of a new catheter is contraindicated or is not feasible, specimens should be collected using aseptic techniques with the urine obtained through a properly disinfected collection port. Urine samples should never be obtained from a collection bag.

NOTE: If more than one pathogen is identified, each should be present at the colony counts noted above to be considered pathogens. In general, if more than 2 bacterial pathogens are identified in an admission urine culture at the predefined colony counts, the sample should be considered contaminated (unless one of the pathogens is also identified in a blood culture).

NOTE: A subject can be enrolled before the urine culture results are available if it is likely to be positive (based on clinical findings and urinalysis).

Sepsis secondary to cIAI or cUTI

The investigator should confirm if the subjects meet the following diagnosis for sepsis upon the study entry in addition to the one of diagnostic criteria for their primary infection. Subjects don't need to meet the criteria for sepsis to be enrolled into this study. However for subjects with sepsis, investigators should also follow the procedures for sepsis as determined in this protocol.

A. Definition

Sepsis is defined as a systemic inflammatory response syndrome induced by infection, with microbiologically documented.

B. Diagnostic Guidelines

Subjects should have clinical signs defined below and meet the following microbiologic criteria;

1. Clinical:

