8.5.2 Efficacy Analysis Population

Two populations, the MITT and the ME populations, will be used for the analysis of efficacy data in this study. The ME population will serve as the primary population for efficacy analyses in this study.

The MITT population is defined as all enrolled subjects who receive at least one dose of IV study therapy. In this study, this is identical with the ASaT population. The ME population is a subset of the MITT population that excludes subjects due to major deviations from the protocol that may substantially affect the results of the efficacy analyses. Potential deviations that may result in the exclusion of a subject from the ME population include the following:

1. The subject fails to meet the protocol definition of cIAI or cUTI
2. The subject had significant violations of inclusion/exclusion criteria that could impact the efficacy assessment (e.g., receipt of previous or concurrent systemic antibacterial therapy beyond those allowed per protocol)
3. The subject received less than 96 hours of IV study therapy (16 infusions)
4. (cIAI only) The subject's pre-study/post-operative culture from the site of infection fails to grow at least 1 gram-negative enteric(s) and/or anaerobic pathogen(s) commonly isolated in IAI. (Note: Subjects who fail to grow a single gram-negative enteric and/or anaerobic pathogen from the site of infection are excluded from the ME population. That is, subjects with only gram-positive pathogens identified will be excluded, as well as those who do not grow any pathogens.)

(cUTI only) The subject's pre-study urine culture fails to grow at least 1 gram-negative and/or anaerobic, pathogen at sufficient quantity specified in the inclusion criteria (See Section 5.1.2 for details)

The composition of the ME population at each time point of interest will be made prior to the database lock and will be documented in a separate memo.

Details on the approach to handling missing data are provided in Section 8.6.

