8.6.2 Statistical Methods for Efficacy Analyses

Missing values

In the analyses using the ME population, any subject with missing or indeterminate assessments for a specific endpoint (clinical or microbiological response) at any particular visit will be excluded from the assessment of that response at that time point. Exceptions follow:

1. (cIAI only) Subjects with a missing culture in the setting of a favorable clinical response: In such subjects, even in the setting of a missing culture at a particular time point, a favorable microbiological response will be presumed from the clinical response (i.e., "presumptive eradication").
2. Subjects discontinuing IV study therapy due to lack of efficacy (i.e., withdrawals with subsequent non-study antibiotic therapy, subjects requiring therapy beyond 14 days), including death due to index infection:
 - These subjects will be considered to be "failures" with respect to clinical response at the time of discontinuation and all subsequent time points post discontinuation, irrespective of whether the clinical response is listed as "indeterminate".
 - These subjects will be considered to have presumed persistence with respect to microbiological response at the time of discontinuation and all subsequent time points post discontinuation, irrespective of whether the microbiological response is listed as "indeterminate."

In the analyses using the MITT population, missing or indeterminate clinical or microbiological responses will be considered failure.

Proportions of subjects with favorable clinical/microbiological responses

A 95% CI based on the method of Agresti and Coull will be provided for the proportion of subjects with cIAI in the ME population achieving favorable clinical response at the EOT visit. The same analysis will be performed for the proportion of subjects with cUTI in the ME population achieving favorable microbiological response at the EOT visit. The same measures at the TOC visit will also be analyzed in the same manner. Supportive analysis using the MITT population will also be performed.

Table 18 summarizes key efficacy analyses.

Table 18 Analysis Strategy for Key Efficacy Variables

Endpoint/Variable (Description, Time Point)	Primary vs. supportive approach [†]	Statistical Method	Analysis Population	Missing Data Approach
Primary objectives				
Proportion of subjects with cIAI achieving favorable clinical response at the EOT visit	P	Agresti and Coull	ME	Data as observed [‡]

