	S	Agresti and Coull	MITT	Missing = Failure
Proportion of subjects with cUTI achieving favorable microbiological response at the EOT visit	P	Agresti and Coull	ME	Data as observed [§]
	S	Agresti and Coull	MITT	Missing = Failure
Secondary objectives				
Proportion of subjects with cIAI achieving favorable clinical response at the TOC visit	P	Agresti and Coull	ME	Data as observed [‡]
	S	Agresti and Coull	MITT	Missing = Failure
Proportion of subjects with cUTI achieving favorable microbiological response at the TOC visit	P	Agresti and Coull	ME	Data as observed [§]
	S	Agresti and Coull	MITT	Missing = Failure

[†] P = primary, S = supportive

[‡] Subjects discontinuing IV study therapy due to lack of efficacy will be considered failures with respect to their clinical response. In subjects with missing culture in the setting of a favorable clinical response, a favorable microbiological response will be presumed from the clinical response.

[§] Subjects discontinuing IV study therapy due to lack of efficacy will be considered persistence with respect to their microbiological response.

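### The supportive MITT analysis of cUTI microbiological response scores dosed subjects with no baseline uropathogen as failures, capping the rate at one minus their unstated share

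*Combined protocol and SAP*

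**What the plan says.** Section 8.5.2 sets the supportive population: "The MITT population is defined as all enrolled subjects who receive at least one dose of IV study therapy". It equals the safety population and carries no baseline-pathogen condition. For this population section 8.6.2 adds: "In the analyses using the MITT population, missing or indeterminate clinical or microbiological responses will be considered failure". Table 18 applies that rule to the cUTI row "Proportion of subjects with cUTI achieving favorable microbiological response at the EOT visit" (primary objective) and to the matching TOC row (secondary objective).

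Section 5.1.2 permits dosing before the culture is known: "A subject can be enrolled before the urine culture results are available if it is likely to be positive". The plan expects some of these cultures to disappoint, because section 8.5.2 lists among the grounds for exclusion from ME a subject whose "pre-study urine culture fails to grow at least 1 gram-negative and/or anaerobic, pathogen at sufficient quantity specified in the inclusion criteria".

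Section 4.2.3.2.1.2 has microbiological response rated pathogen by pathogen against the baseline isolates. In Table 6 (cUTI, EOT), eradication means that the EOT urine culture "shows eradication of the uropathogen" present at entry, and a favorable overall response needs this for all baseline pathogens. Table 7 has the corresponding requirement at TOC. Table 17 limits presumptive eradication to cIAI.

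**The concern.** A cUTI subject with no baseline uropathogen has no pathogen to rate and cannot reach a favorable response. Table 6 does not name this case. Either no response exists, or the subject falls under the last Indeterminate item, "Any other circumstance which makes it impossible to define the microbiological response". The cIAI table is explicit where the cUTI table is silent: Table 4 lists "Entry culture at the site of infection either not obtained or no growth" as Indeterminate. Both routes end in failure under the MITT rule.

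This is not ordinary missing data. The endpoint is undefined at baseline for such a subject, so neither eradication nor persistence can be observed.

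MITT is the only supportive analysis of the cUTI primary endpoint. Its use is to show whether the ME result survives the ME exclusions. If the MITT rate comes out low, the reader cannot tell whether pathogens persisted, follow-up cultures were missing, or there was no organism to begin with.

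**Working it through.** **Inputs**

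- Section 8.9: 40 subjects enrolled per cohort, at least 70% expected in ME, so 0.70 × 40 = 28 in ME and 12 outside; 26 of 28 favorable.
- Sections 8.6.2 and 8.9: 95% Agresti-Coull interval.
- f, the share of dosed cUTI subjects with no baseline uropathogen: not given in the documents. Assumed range 0% to 30%.

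**Reproducing the plan's figure**

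With z = 1.96, n' = n + z² and p' = (x + z²/2)/n'; the limits are p' ± z√(p'(1 − p')/n'), truncated to 0–100%. For 26/28, n' = 31.84, p' = 27.92/31.84 = 0.877 and the half-width is 0.114, giving 92.9% (76.3, 99.1) as stated. All eight rows of Table 19 reproduce to 0.1 point.

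**Ceiling**

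Let r be the response rate among subjects who have a baseline uropathogen. Then MITT rate = (1 − f) × r, with maximum 1 − f at r = 1. For 40 dosed:

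| f (assumed) | No uropathogen | Ceiling (95% CI) | Expected MITT rate if r = 26/28 |
|---|---|---|---|
| 0% | 0 | 40/40 = 100% (89.6, 100) | 92.9% |
| 5% | 2 | 38/40 = 95% (82.6, 99.5) | 88.2% |
| 10% | 4 | 36/40 = 90% (76.4, 96.6) | 83.6% |
| 20% | 8 | 32/40 = 80% (65.0, 89.8) | 74.3% |
| 30% | 12 | 28/40 = 70% (54.5, 82.0) | 65.0% |

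The cap applies to the point estimate; the upper confidence limit can lie above it. The last row requires every one of the 12 non-ME subjects to lack a uropathogen. The planned 30% in fact pools all exclusion reasons and non-evaluability at EOT.

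**Confounding**

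Take the plan's 26 favorable in ME and suppose none of the other 12 is rated favorable. MITT then reads 26/40 = 65.0% (49.5, 77.9) whatever the reason. Let k of the 12 have no baseline uropathogen; the rate among subjects with a pathogen is 26/(40 − k):

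| k | Rate among subjects with a pathogen (95% CI) |
|---|---|
| 0 | 26/40 = 65.0% (49.5, 77.9) |
| 4 | 26/36 = 72.2% (55.9, 84.3) |
| 8 | 26/32 = 81.3% (64.3, 91.5) |
| 12 | 26/28 = 92.9% (76.3, 99.1) |

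One reported MITT figure fits all four.

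**The case against.** The strongest reply is that this is a disclosed worst-case analysis, set beside a restrictive ME analysis and labelled supportive. The bias can only lower the rate. The trial is single-arm estimation with no success threshold, and the primary population already requires a qualifying organism. All of that stands, and it limits the severity. It does not make the supportive rate interpretable: a conservative bias of unknown size could wrongly suggest that the ME exclusions inflated efficacy.

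A second reply is that f may be small. Pyuria is required, early enrollment is allowed only when a positive culture is likely, and prior effective antibiotics are restricted. That is fair. The isolated effect at f = 5% or 10% is a fall from 92.9% to 88.2% or 83.6%, and the constant 65.0% in the second table depends on assuming no favorable subject outside ME. Subjects with only a gram-positive uropathogen are outside ME yet can be rated favorable in MITT, so they must not be counted in f.

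Third, the culture data are on the eCRF and ME membership is to be recorded in a memo before database lock. But nothing commits the sponsor to report f, and the cUTI culture criterion for ME pools gram-positive-only growth with no growth.

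Finally, a colony-count threshold also removes subjects with sub-threshold growth, whom Table 6 might allow to be rated, since its counts are given as examples. The threshold is nevertheless the protocol's own definition of a positive baseline urine culture, and section 5.1.2 also says how to treat contaminated specimens.

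**Conclusion.** The concern holds. Under the plan as written, a dosed cUTI subject with no baseline uropathogen is a microbiological failure in MITT at both EOT and TOC, and the rate is bounded by 1 - f. The step through Table 6 is by implication, because the table omits the no-growth case, but a missing response and an indeterminate one give the same result.

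The size depends entirely on f, which is assumed here: a ceiling of 95% to 70% for f of 5% to 30% with 40 dosed, the upper end being an outer bound if the 70% ME expectation is met. The effect is confined to the two supportive cUTI rows and drives no decision. It should be fixed, at moderate priority.

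**What to change.** For the cUTI microbiological rows of Table 18, at EOT and TOC, define the supportive population as dosed subjects with at least one baseline uropathogen, gram-negative or gram-positive, that meets the colony-count thresholds of section 5.1.2. Do not borrow the narrower gram-negative or anaerobic criterion used for ME. Within this population keep missing or indeterminate as failure, and report the number of dosed cUTI subjects without a baseline uropathogen. Keep the all-treated MITT for clinical response.

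The cost is SAP wording and one derived flag from culture data already collected; section 8.0 allows such a change through the supplemental SAP before database lock. The drawback is a smaller supportive denominator, for example 36 instead of 40 if f is 10%.

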- Further increase in transaminases to ≥ 8 X ULN that is not anticipated from their underlying medical condition.
- ALT or AST ≥ 3 X ULN [with at least 50% increase from transaminase values collected at Day 1] and new onset of clinical signs and symptoms of fatigue, nausea, vomiting, right upper quadrant pain or tenderness, fever (defined as oral temperature $\geq 38.0^{\circ}\text{C}$), rash, and/or eosinophilia ($> 5\%$)
- Clinically significant worsening of liver function associated with further transaminase elevations in a subject with abnormal transaminase levels already meeting the above criteria (i.e., ≥ 8 X ULN; ALT or AST ≥ 3 X ULN [with at least 50% increase from transaminase values collected at Day 1] and new onset of clinical signs and symptoms listed) at baseline.

The subject will discontinue from study therapy, but will continue to participate in the study and will be assessed according to all study planned study procedures through the final study visit and will be evaluated for blood chemistry and hematology (including, at minimum, ALT, AST, alkaline phosphatase, bilirubin (direct + indirect) and creatine phosphokinase) until values return to within normal range. The trial site guidance for assessment and follow up of liver function test (LFT) elevations can be found in the Investigator Trial File Binder.

- A post-baseline decline in estimated or actual creatinine clearance to a value of less than 15 mL/min.
- The subject requires initiation of hemodialysis or peritoneal dialysis.
- The subject has a confirmed positive serum or urine (sensitivity of < 25 million IU/L is required if using urine test) pregnancy test.
- A physician investigator feels it is in best interest of the subject to discontinue for any reason, including, but not limited to, the need for alternative non-study antibacterial therapy.

For subjects who are discontinued from treatment but continue to be monitored in the trial, all visits and procedures, as outlined in the trial flowchart, should be completed.

Discontinuation from treatment is “permanent.” Once a subject is discontinued, he/she shall not be allowed to restart treatment.

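### The rule that a lack-of-efficacy stop stays a failure at later visits is written for ME only, so the supportive MITT analysis of cIAI clinical response at TOC can count some rescued subjects as cures (minor)

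*Combined protocol and SAP*

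**What the plan says.** The missing-values text in section 8.6.2 starts with one population: "In the analyses using the ME population, any subject with missing or indeterminate assessments for a specific endpoint" is left out of that assessment at that visit. Two exceptions follow. The second covers subjects who stop for lack of efficacy, glossed as "withdrawals with subsequent non-study antibiotic therapy, subjects requiring therapy beyond 14 days" and including death from the index infection. They are failures "with respect to clinical response at the time of discontinuation and all subsequent time points post discontinuation", with a parallel rule of presumed persistence for microbiological response.

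MITT is then handled in its own sentence: "In the analyses using the MITT population, missing or indeterminate clinical or microbiological responses will be considered failure".

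Table 18 has the same split. Its footnote reads "Subjects discontinuing IV study therapy due to lack of efficacy will be considered failures with respect to their clinical response", and the mark for it sits on the ME cells (a parallel footnote covers cUTI). The MITT cells say "Missing = Failure" and carry no mark.

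Two other places bear on the point. Section 8.5.2 states: "The MITT population is defined as all enrolled subjects who receive at least one dose of IV study therapy". Section 5.8.1 says that "For subjects who are discontinued from treatment but continue to be monitored in the trial, all visits and procedures" in the flow chart should be completed.

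Table 3 defines Cure at TOC for cIAI by three conditions: the signs and symptoms present before therapy have resolved, no further IV antibiotic is needed, and no unplanned surgery or percutaneous drainage has taken place.

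**The concern.** MITT is the supportive check on the ME result. It should be at least as strict as ME for any subject who is in both. As written, it relies on a lack-of-efficacy stop showing up as a missing or indeterminate rating. The protocol asks stopped subjects to keep attending, so some will have an observed TOC rating instead. If that rating is Cure because another antibiotic worked, nothing in the MITT rule changes it.

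The trial has a single arm, so no comparator offsets such a credit. The MITT TOC estimate would then include some effect of the rescue drug, and one subject could be a failure in ME and a success in MITT.

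**Working it through.** **1. Scope of the rule.** The two populations compare as follows for a subject who stops for lack of efficacy.

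| TOC rating | ME (8.6.2, Table 18) | MITT (8.6.2, Table 18) |
|---|---|---|
| Missing or Indeterminate | failure (exception 2) | failure (MITT sentence) |
| Failure | failure | failure |
| Cure | failure (exception 2, footnote) | favourable; no rule changes it |

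Only the last row differs. No text elsewhere extends exception 2 to MITT.

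**2. Can such a subject be rated Cure under Table 3?**
- Unplanned surgery or drainage: no. The procedures condition excludes it.
- Additional IV antibiotic still needed at TOC: no.
- IV rescue finished before TOC: unclear. The antibiotic condition is in the present tense and the procedures condition in the perfect, so the former can be read as of the visit. TOC is 5 to 9 days after IV study therapy ends (section 7.1.5.3). The guideline cited in section 4.2.2.3 gives 5 to 7 days of treatment for most cIAI. A finished course is possible, but the window is tight.
- Oral rescue: yes, if signs have resolved. Table 3 restricts IV antibiotics only, whereas exception 2 covers non-study antibiotics by any route.

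**3. Other endpoints.** At EOT the visit falls within 24 hours of the last study dose and Table 2 has the same IV condition, so rescue has little time to act. For cUTI, Table 6 footnote c presumes persistence after a stop for clinical failure where culture does not confirm it or none was taken. Table 7 footnote c ties sustained eradication at TOC to eradication at EOT. The cUTI row is therefore largely protected.

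**4. The plan's own interval.** Agresti-Coull with z = 1.96: ñ = n + z², p̃ = (x + z²/2)/ñ, limits p̃ ± z√(p̃(1 − p̃)/ñ). For 26/28: ñ = 31.84, p̃ = 27.92/31.84 = 0.877, half-width 0.114, giving 76.3% to 99.1%, as stated in section 8.9. All eight rows of Table 19 reproduce. They concern ME at EOT and do not change.

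**5. Size per subject.** Each Cure that exception 2 would have made a failure adds 1/N to the MITT rate: 1/30 = 3.3, 1/40 = 2.5, 1/50 = 2.0 points. The cohort sizes come from Table 19.

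**6. Illustration at N = 40**, assuming 34 cures that do not depend on rescue:

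| Rescued subjects rated Cure | MITT TOC rate (95% CI) |
|---|---|
| 0 (or rule extended to MITT) | 34/40 = 85.0% (70.5, 93.3) |
| 1 | 35/40 = 87.5% (73.4, 95.0) |
| 2 | 36/40 = 90.0% (76.4, 96.6) |

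**7. How many subjects?** The documents give no count of lack-of-efficacy stops. As a rough guide, the phase II cIAI study (PN004) had 81 − 78 = 3 of 81 (3.7%) without a favourable clinical response at the end of IV therapy (250 mg arm, ME). Applied to 40 subjects this gives 40 × 3/81 = 1.5, with a chance of at least one of 1 − (78/81)^40 = 78%. At 30 and 50 the expected numbers are 1.1 and 1.9. Only those later rescued without a barred procedure and then rated Cure matter. I assume 0 to 2: 0 to 6.7 points at N = 30, 0 to 5.0 at 40, 0 to 4.0 at 50.

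**The case against.** The strongest reply is that the ratings already do most of this work. Table 3 excludes cIAI subjects managed by re-operation or drainage. Entry requires an infection that needs hospital IV treatment, so IV rescue is the natural case, and on an ordinary reading a subject who needed it is not a Cure. Table 3 Failure also refers to insufficient response to the study therapy. An unclear case can be rated Indeterminate, which MITT counts as failure. All of this stands and narrows the route considerably. It does not close it: oral rescue is not mentioned, the tense of the antibiotic condition is open, and the rest of the Failure definition turns on signs that a recovered subject no longer has.

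A second reply is that exception 2 is itself a missing-data rule and does not say outright that it overrides an observed Cure in ME. That is fair. The Table 18 footnote is worded without that limit, which supports the override, but the wording should be made explicit for both populations.

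A reader might infer more than the documents support:
- That any subject rescued by another antibiotic can count as a cure. Table 3 rules out much of this.
- That MITT is the only analysis holding early failures. Section 8.5.2 lists fewer than 16 infusions as a potential reason for exclusion from ME, not an automatic one.
- That every stopped subject will have a TOC rating. Section 7.1.4.1 only encourages continued follow-up, and a missing rating is already a failure in MITT.

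**Conclusion.** The gap is real and small. The text of section 8.6.2 and the Table 18 footnotes agree in giving the lack-of-efficacy rule to ME alone. As a result, a cIAI subject rescued orally, or by an IV course completed before TOC on one reading of Table 3, can be favourable in MITT while a failure in ME.

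Its reach is one supportive analysis of one secondary endpoint, in a study that estimates and does not test. A reader should not take it to affect the primary ME estimates or the planned precision. The shift of 0 to 5 points at N = 40 rests on the assumed 0 to 2 subjects, and zero is a plausible value. The severity is minor.

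**What to change.** State in section 8.6.2 that exception 2 applies to both the ME and MITT analyses: a lack-of-efficacy discontinuation counts as failure, or presumed persistence, at that and all later visits, whatever rating is recorded. In Table 18, add only the lack-of-efficacy part of each footnote to the MITT rows. The other part of the cIAI footnote, which presumes a favourable microbiological response when a culture is missing, should stay with ME because it would conflict with the MITT rule.

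Section 8.0 already provides a supplemental SAP for changes before database lock, so this needs no new data and no change to conduct. The cost is a few lines of text and a possibly slightly lower MITT rate at TOC. If the sponsor already intends this handling, writing it down avoids a choice after the data are seen.
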